**Table 18.13 Protocol for sensitive and precise Molecular Tumor Burden (MTB) estimation.**

Step	Methodological details
1	
For each cfDNA sample, obtain independent estimates of tumor purity:
 

a) using LP WGS CNAs and fragment length,

b) CNVs from the targeted panel data,

c) mutation variant allele fractions (VAFs).

 
Since we have several independent estimates of tumor purity, each with its own confidence interval, we combine them with a weight that is inversely proportional to their variance.

2	
Convert the sample tumor purity to DNA tumor fraction:
 $TF = (\text{purity} * \text{ploidy}) / (\text{purity} * \text{ploidy} + 2[1 - \text{purity}])$ 
This step requires an estimate of tumor ploidy, which can be challenging for samples with low tumor purity. In cases in which the ploidy is not known, we can use a representative ploidy value for ploidy value tumor cells (e.g., cHL median 3.1)(26).

3	
Convert DNA tumor fraction (TF) to units of Human Genome Equivalents (hGE):
 $\#hGE / ml \sim (TF * mDNA) / (mHG * vTube)$ 
Where mDNA is the mass of DNA from sequencing library preparation, mHG is the mass of a human genome (~6.5e-3 ng), and vTube is the volume of blood collected (3ml for the preliminary data shown here).

**4. Case Selection (if applicable)**

As a first step, we will analyze the first half of patients enrolled to the study, who will have sufficient follow-up and a full set of specimens - baseline, C3D1, EOT, relapse (if applicable). We anticipate that about 80% of patients will have the full set of serial specimens. As of May 15, 2022, there were currently 400 patients with paired baseline, C3D1, EOT, and paired normal buffy coat samples banked at the SWOG biorepository. We will also analyze patients who progress on therapy but have baseline and at least one on-treatment sample (and paired baseline buffy coat specimen). We will reserve the samples from patients enrolled to the second half of the study for validation purposes and/or to further interrogate preliminary findings from the initial analysis.

**5. Methods**

**d. Statistical Design and Underlying Assumptions**

**Endpoints and Definitions**

The primary clinical endpoint is progression-free survival (PFS). Secondary clinical endpoints include complete response (CR), event-free survival (EFS), and overall survival (OS).

Progression-free survival (PFS) is defined as time from date of registration to date of first observation of progressive disease according to the 2014 Lugano classification, or death due to any cause. Patients last known to be alive and without report of progression are censored at date of last contact. Complete response (CR) at the end of therapy is defined according to the 2014 Lugano classification (e.g. Deauville score 1-3). Overall survival (OS) is time from date of registration to date of death due to any cause. Patients last known to be alive are censored at date of last contact. Event-free survival (EFS) is defined as time from date of registration to date of first occurrence of EFS event. Patients last known to be alive and without EFS event are censored at date of last contact. EFS Events are defined as:

- Disease progression/relapse
- Administration of non-protocol specified systemic anti-lymphoma therapy (i.e. salvage therapy) at any time after initiation of protocol therapy.
  - Administration of non-protocol specified systemic anti-lymphoma therapy for residual or relapsed Hodgkin lymphoma (whether or not confirmed by biopsy) in the absence of formal progression of disease according to the Lugano classification
- Administration of any non-protocol specified radiation therapy at any time after initiation of protocol therapy:
  - Administration of radiation therapy in a patient who was not declared eligible for radiation therapy at registration
- Administration of radiation in a patient who was declared eligible for radiation therapy but does not meet protocol-specified criteria for use of radiation

The biomarker analysis team at DFCI/Broad will be blinded to treatment arm and patient outcomes. Data standardization and coding will be completed by DFCI/Broad and prior to analysis of the outcome data. The SWOG biostatistical team ([name], [name]) will assess the relationship between genetic alterations or MTB and patient outcomes.

The S1826 study will accrue 470 eligible patients per arm. Based on previous data, the 2-year PFS after BV-AVD is estimated to be approximately 82%. An exponential cure rate model is assumed for both arms. In addition, among the fraction of patients with disease progression, a hazard ratio of 1.67 is assumed between the arms. Under the above assumptions, for the proposed initial sampling size of 400 patients (accrued during the first half of study accrual) with samples and designed follow-up, we assume that there will be a total of 94 PFS events across both arms under the alternative hypothesis. Hence, we believe most power calculations are conservative.

Objective 1: To test if the treatment effect of N-AVD versus BV-AVD on PFS depends on specific genetic alterations, we will power this analysis using 9p24.1 amplification, which are characteristic in cHL. We assume 400 patients with evaluable samples and similar follow-up by study design. Based on our prior work, 9p24.1 amplification will be present in 50% of advanced stage cHL patients.(18) Based on its established prognostic impact in standard frontline chemotherapy-based treatment of cHL, it is assumed that 9p24.1 alteration will be positively associated with PFS after N-AVD but not after BV-AVD. A two-sample, two-sided level .05 of a Cox Regression score test of the interaction for patients with and without 9p24.1 amplification has power of approximately 80% to detect an interaction ratio of hazard ratios of 3.3. In addition, we will test the prognostic association in each of the treatment groups. Testing the prognostic association within the BV-AVD group, a two-sample log-rank test for patients as defined by 9p24.1 amplification among BV-AVD patients has power of approximately 90% to detect a hazard ratio of 2.5. In both analyses, the magnitude effect sizes are critical for interpretation and 95% confidence intervals will be presented. In addition, we will use descriptive statistics to characterize the frequency of each type of genetic alteration at baseline in the S1826 cohort, and evaluate associations with outcome.

We will use descriptive statistics to characterize the frequency of each type of genetic alteration at baseline in the S1826 cohort. We will investigate the impact of each identified recurrent genetic alteration on PFS in a univariable model. Specific alterations of interest that will be formally assessed are JAK/STAT pathway mutations (i.e. SOCS1, STAT6), EBV-associated alterations, and MSI-associated alterations. We will also evaluate the interaction between 9p24.1 alterations and JAK/STAT mutations and impact on PFS. Additionally, we will use Elastic Net(19) to select, out of all the genetic alterations, and clinical and demographic features, the ones important for the model, by using both linear and quadratic penalty components.

We will also assess differences in PFS for all of the above-mentioned prognostic factors (including 9p24.1 alteration and JAK/STAT mutations), now incorporating the randomized treatment assignment (N-AVD vs BV-AVD). Our prior studies(20, 21) suggest that high-level 9p24 CNAs may be associated with a more favorable outcome in the N-AVD, but not the BV-AVD, treatment arm of S1826. We will first examine treatment by the individual alterations or dysregulated pathways, and then apply the Elastic Net model with the treatment arm as an additional available covariate. Next, we will allow the Elastic Net to also use clinical and demographic features. Thus, the final models will be able to combine features detected in the ctDNA, the randomized treatment arms, and the patient's clinical and demographic information. We will also assess whether specific molecular features are selectively predictive in one of the treatment arms.

We appreciate the sample size is limited to detect complex associations hence results will primarily hypothesis generating. However, to yield the most interpretable results we plan to pre specify potential alterations and clinical factors (age, IPS, Stage, extranodal involvement) and key tuning parameters for the elastic net algorithm. Model complexity will be selected by generalized cross-validation. By fully specifying the statistical algorithm we can then assess the statistical strength of the individual molecular components by utilizing the appropriate resampled permutation tests.

**Objective 2:** Assess the prognostic significance of MTB in patients treated with either N-AVD or BV-AVD. The primary MTB analysis will consider the change in MTB between baseline and C3D1, the cut-point will be the 2-log change. We anticipate 70% of patients will achieve the 2-log change (including those patients who transition to unmeasurable). Testing the prognostic association combining but stratified by treatment group, a two-sample log-rank test for patients landmarked at C3D1 has a power of approximately 93% to detect a hazard ratio of 2.1. The expected width of the 95% confidence interval for this effect is (1.4,3.2). Secondary analyses will consider MTB at baseline on the continuous log scale. In addition, if for the continuous scale there is a significant association with outcome, adaptive split point optimization will be considered. The algorithm to select cut point will be fully specified including the minimum fraction of patients above will be set at 20% of sample size prior to analysis of any outcome data. Permutation re-sampling will be used to assess significance in the context of this correlated multiple comparison problem (22eg. LeBlanc and Crowley, 1995)

We will characterize the MTB at baseline in units of HGE/ml and assess its prognostic value as a single variable and after adjusting for clinical prognostic features/stratification factors age (<18, 18-60, >60 yrs.) and International Prognostic Score (0-3 vs 4-7)(2333). We will also consider baseline MTB categorized by a median cut-point.

At subsequent time points, we will evaluate changes in MTB at both C3D1 and EOT compared to baseline. In cHL and other lymphoid malignancies, a 2-log (100-fold) decrease in MTB after 2 cycles of therapy (C3D1) predicts outcome(2434). We will use this parameter in S1826 trial patients as a binary covariate. Outcomes of interest will include both PFS (the primary endpoint of S1826) and achievement of CR at EOT as determined by PET/CT. We will characterize the magnitude of change descriptively for those who exhibit progressive disease within the 6 cycles of therapy and those who do not, and also by categories of response for those who do not progress. These measures look at per patient MTB changes, and do not rely on the baseline threshold(s) defined above.

We will initially investigate change in MTB in a univariable setting but will also use multivariable models incorporating other demographic and clinical features from diagnosis to understand how these additional features may modify the interpretation of changes in MTB. To more clearly consider the relationship between changes in MTB and PFS outcomes, we will also perform a landmark analysis of PFS including only those patients who remain alive without progression at EOT. All assessments of MTB and PFS will rely on log rank tests in the setting of a single threshold for all patients or stratified log rank tests in the setting of customized thresholds for the age and IPS risk score strata defined in the protocol, and Cox proportional hazards models for the multivariable setting, using either stepwise selection or a lasso approach. Again, to assess overall multivariable performance, variables and cut points will be specified prior to using the Lasso. In addition, it is recognized that cross-validated partial likelihood is unstable; therefore, model selection (complexity) will use generalized cross-validation.

We will specifically assess the PPV/NPV of detectable ctDNA at EOT and compare this to the gold standard EOT PET-CT scan response according to the 2014 Lugano Classification. We assume that approximately 20% of patients will be ctDNA positive at EOT, and 10% will be PET-CT positive (Deauville Score 4-5) at EOT. With approximately 200 patient samples per arm, then the PPV for either of those measures can be estimated to within +/- 11% (95% confidence interval) for the case with 20% ctDNA positive. Analogous results hold for PET-CT and NPV.

e. Materials Handling

Frozen samples will be shipped on dry ice from the SWOG biorepository at Nationwide Children's Hospital to DFCI/Broad for analysis.

f. Funding

BIQSFP funding has been secured from NCI CTEP for the Translational Medicine analysis. Additional funding support will be provided by BMS and/or the TM investigators internal institutional funding.

g. References

- 1 Song Y, et al. A single-arm, multicenter, phase 2 study of camrelizumab in relapsed or refractory classical Hodgkin lymphoma. *Clin Cancer Res.* 2019 Aug 2016. doi: 2010.1158/1078-0432. CCR-2019-1680. [Epub ahead of print], 2019.

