AVD or BV-AVD) regardless of the result of the primary analysis and can inform the design of the next cHL clinical trial in the cooperative groups (e.g. response adapted therapy using ctDNA and/or PET).

We hypothesize that ctDNA will identify characteristic alterations of chromosome 9p24.1 (i.e. amplification) and genes (i.e. JAK/STAT pathway genes - SOCS1, STAT6) that result in overexpression of PD-1 ligands in cHL and that these genetic features will be selectively associated with favorable response and PFS in patients treated with N-AVD,(24, 29) but not after BV-AVD. Therefore, we are testing if treatment effect of N-AVD versus BV-AVD on PFS depends on 9p24.1 and specific gene alterations. Additionally, we hypothesize that MTB will be prognostic for PFS in patients treated with either N-AVD or BV-AVD (i.e. irrespective of regimen): (1) baseline MTB will be prognostic for PFS, (2) interim on-treatment kinetic changes in MTB (i.e. achievement of 2-log drop in MTB after 2 cycles) will be prognostic for PFS, and (3) MTB at EOT will have superior PPV and NPV to 5-point PET-CT at interim and EOT.

c. Experimental Approach and Assays

1. Sample Collection

Patients have 20mL of whole blood collected at baseline, on C3D1, at EOT, and at the time of relapse or progression (if applicable) in BCT cell-free DNA Streck tubes. Samples are shipped to the SWOG central biorepository where the whole blood is separated into plasma and buffy coat, yielding 10-12mL of plasma per time point, separated into 1mL aliquots. Samples are stored at -80C. Frozen samples will be shipped on dry ice from the SWOG biorepository to DFCI/Broad.

2. Collection Kits / Order of Sample Collection / Sample Collection and Submission Instructions

3. Description of Assay or Methods

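### The pooled, arm-stratified test of MTB response at C3D1 cannot by itself show that the marker is prognostic irrespective of regimen; arm-specific and interaction estimates should be added

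*Combined protocol and SAP*

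**What the plan says.** The background to the ctDNA study (18.13b) sets out the MTB hypothesis: "we hypothesize that MTB will be prognostic for PFS in patients treated with either N-AVD or BV-AVD (i.e. irrespective of regimen". The three components listed are baseline MTB, the 2-log drop after two cycles, and MTB at EOT.

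Under Objective 2 of 18.13d the primary MTB analysis is the 2-log change from baseline to C3D1. It is tested thus: "Testing the prognostic association combining but stratified by treatment group, a two-sample log-rank test for patients landmarked at C3D1". The plan says this test "has a power of approximately 93% to detect a hazard ratio of 2.1", and adds: "The expected width of the 95% confidence interval for this effect is (1.4,3.2". The expected marker split is given as "We anticipate 70% of patients will achieve the 2-log change".

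The rest of Objective 2 covers baseline MTB on a continuous scale and by cut-point, multivariable Cox models with demographic and clinical features, an EOT landmark analysis, and log-rank tests stratified by age and IPS. None of these is an MTB hazard ratio within each arm or an MTB-by-treatment interaction. The one per-arm item is the precision of PPV and NPV for detectable ctDNA at EOT, which is a different measure at a different time and not a test.

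Objective 1 handles 9p24.1 amplification differently. It specifies a Cox score test of interaction and continues: "In addition, we will test the prognostic association in each of the treatment groups". It also says that confidence intervals will be presented. The later sentence in Objective 1 about features that matter in one arm only refers to the genetic alterations, not to MTB.

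**The concern.** The hypothesis concerns two arms; the test concerns their average. A log-rank test stratified by treatment sums the within-arm scores and divides by the summed variance. It therefore estimates an event-weighted mean of the two log hazard ratios. Rejecting its null says that this mean is not zero. A strong effect in one arm and none in the other can produce that.

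This matters because 18.13b intends the results to inform later trials that adapt treatment to ctDNA response. BV-AVD is expected to contribute more events and so carries more weight. A pooled result driven by BV-AVD could be carried over to N-AVD patients, for whom the data might show little.

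**Working it through.** **Inputs.** From 18.13d: 400 patients, about 200 per arm; for events, "we assume that there will be a total of 94 PFS events across both arms under the alternative hypothesis"; 70% achieve the 2-log change and 30% do not; design hazard ratio (HR) 2.1. Two-sided 0.05 is stated only for Objective 1 and is assumed here for Objective 2. The arm split of events is not given. It is taken as equal (47/47), or as about 58:42 for BV-AVD:N-AVD (55/39). The uneven split comes from a cure model with cure fractions 70% and 74% and hazard ratio 1.67 (Section 11.1) and 2-year control PFS of 82% (18.13d).

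**1. The plan's own figure.** Power = Φ(ln HR × √(D·p·(1−p)) − 1.96).
- D = 94, p = 0.30: √19.74 = 4.443; 0.742 × 4.443 = 3.296; power Φ(1.336) = 90.9%.
- With p set to the non-achievers' share of events at HR 2.1, 0.63/1.33 = 0.474: power 94.9%.
- 95% CI, exp(0.742 ± 1.96/4.443) = 1.35 to 3.26; with p = 0.474, 1.40 to 3.15.

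These bracket the stated 93% and agree with the stated interval of 1.4 to 3.2. A simulation of the treatment-stratified log-rank test (5,000 runs, 200 per arm, cure model, landmark at day 56, about 92 events of which about 6 precede the landmark) gives 91.4%. The plan's power figure is sound for an effect common to both arms.

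**2. Effect in one arm only (HR 1.0 in the other).** Pooled ln HR = (event share of that arm) × ln HR.
- Equal split, HR 2.1: 0.5 × 0.742 = 0.371, pooled HR 1.45; 0.371 × 4.443 − 1.96 = −0.31; power 38%.
- BV-AVD only, 55/39: (55/94) × 0.742 = 0.434, pooled HR 1.54; power 49%.
- N-AVD only, 55/39: (39/94) × 0.742 = 0.308, pooled HR 1.36; power 28%.

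Chance that the pooled test is significant:

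| One-arm HR | Equal split, formula | BV-AVD only: formula 55/39; simulation | N-AVD only: formula 55/39; simulation |
|---|---|---|---|
| 2.1 | 38% | 49%; 51% | 28%; 31% |
| 2.5 | 53% | 66%; 68% | 39%; 43% |
| 3.0 | 69% | 81%; 83% | 53%; 59% |

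With the Section 11.1 curve instead (84% 2-year control PFS), 400 patients yield about 51 and 35 events. The figures at HR 2.1 are then 46% and 25%, and at HR 3.0 they are 79% and 48%. On that split, HR 3.5 in BV-AVD and 1.0 in N-AVD gives a pooled HR of exp((51/86) × ln 3.5) = 2.10, which is the design effect, and 88% rejection.

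**3. What the added estimates could show.**
- Within-arm power at HR 2.1: 64% at 47 events. In the simulation, 73% in BV-AVD (about 54 events), 60% in N-AVD (about 39), and 44% for both.
- Interaction at 2.1 versus 1.0, equal split: SE = √(2/(47 × 0.21)) = 0.450; 0.742/0.450 − 1.96 = −0.31; power 38%. The simulation gives 42–43%; the 51/35 split gives 34%.
- Ratio of hazard ratios for 80% power: exp(2.80 × 0.450) = 3.5, or 3.2 with the event-share weights. The plan accepts 3.3 for 9p24.1.
- N-AVD 95% CI at 39 events: a factor of exp(1.96/√(39 × 0.21)) = 2.0 either way.

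**The case against.** A stratified pooled test is a conventional choice when a prognostic effect is expected to run the same way in both arms, and the documents give a reason to expect that. Section 18.13b reports that ctDNA decline is associated with PFS under nivolumab as well as under standard treatment. An HR of exactly 1.0 in one arm is an assumption with no support in the text. The contrast with 9p24.1 also has a reason: that alteration is expected to act differently by arm, so the interaction is the main question there. Finally, samples from the second half of enrolment are reserved for validation. All of this stands, and it makes the one-arm scenario less likely. It does not let the pooled test establish the two-arm hypothesis, and reserving samples does not change what this first analysis can conclude.

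A reader might go further and infer that a one-arm marker would usually be reported as confirmed. The documents do not support that. At the plan's own HR of 2.1 the pooled test would be significant in about 25–51% of such cases. It reaches half only at a one-arm HR of about 2.0–2.1 if the effect is in BV-AVD, and about 2.6–2.9 if it is in N-AVD. Nor does any passage say that a pooled rejection will be reported as showing prognostic value irrespective of regimen; the plan states a hypothesis and names a test.

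**Conclusion.** The point holds as a mismatch between hypothesis and test, and as a minor one: a translational analysis is affected, not the trial's primary result. A significant pooled result shows an effect in at least one arm. With a one-arm effect, the chance of such a result is roughly one quarter to one half at HR 2.1, higher if the effect is in BV-AVD. At HR 3 it is about 80% for BV-AVD only and 48–59% for N-AVD only.

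The figures assume two-sided 0.05 for Objective 2, a 70/30 marker split in both arms, proportional hazards for the marker, and 86 to 94 events split between equal and about 59:41.

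**What to change.** In 18.13d, Objective 2, add to the C3D1, baseline and EOT analyses of MTB and PFS the arm-specific hazard ratios with 95% CIs and the MTB-by-treatment ratio of hazard ratios with its 95% CI, using the Cox model already specified for 9p24.1. State that any conclusion that MTB is prognostic irrespective of regimen will rest on the arm-specific estimates and their intervals, and that a non-significant interaction will not be read as evidence of consistency.

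The second sentence is needed. Suppose agreement were declared whenever both estimates point the same way and the interaction is not significant. With HR 2.1 in BV-AVD and 1.0 in N-AVD, about 61–64% of the significant pooled results would still pass as holding in both arms.

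The cost is SAP wording and one extra model per time point, with no new data. The drawback is imprecision: about 60–73% power per arm and about 40% for the interaction at 2.1 versus 1.0. The conclusion may have to be more cautious, and descriptive until it is checked in the reserved second-half samples.
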